17.4 Additional tables

Table 45. Historic and current antiplatelet treatment according to current NOAC type

		Dabigatran	Rivaroxaban	Apixaban	Edoxaban	Total
Antiplatelet treatments received (all)	Valid N Aspirin Clopidogrel Prasugrel Ticlopidine Ticagrelor Cilostazol Triflusal Dipyridamole					

Document: H:\HOR-Europe\2019\2512352 - Study on anticoagulation management - BI\Proyecto\Estadistica\SAP\SAP_REBELD_version1.0_08072020.docx

Author: [REDACTED] Version Number: Version 1.0
Version Date: [08072020]

Template No.: RWI_TP_BIOS0013 Revision 1

Reference: RWI_WI_BIOS0015

Effective Date: 15Jun2018

		Dabigatran	Rivaroxaban	Apixaban	Edoxaban	Total
	Others N missing					
Time in treatment with antiplatelet agents (in years)	Valid N Mean (SD) Median (Q1-Q3) Min-Max N missing					
Current antiplatelet treatment (at study visit)	Valid N None Aspirin Clopidogrel Prasugrel Ticlopidine Ticagrelor Cilostazol Triflusal Dipyridamole Others N missing					

Table 46. Treatment received at the moment of thromboembolic events (1st part)

		TIA	Ischemic stroke	Hemorrhagic stroke	Embolism systemic	Deep vein thrombosis
Treatment (VKA/NOAC/antiplatelet)	Valid N* No Yes N missing					
VKA	Valid N* No Yes N missing					
Type of VKA	Valid N Acenocoumarol Warfarin N missing					

Document: H:\HOR-Europe\2019\2512352 - Study on anticoagulation management - BI\Proyecto\Estadistica\SAP\S AP_REBELD_version1.0_08072020.docx

Author: [REDACTED] Version Number: Version 1.0
Version Date: [08072020]

Template No.: RWI_TP_BIOS0013 Revision 1

Reference: RWI_WI_BIOS0015

Effective Date: 15Jun2018

		TIA	Ischemic stroke	Hemorrhagic stroke	Embolism systemic	Deep vein thrombosis
NOAC	Valid N* No Yes N missing					
Type of NOAC	Valid N Dabigatran Rivaroxaban Apixaban Edoxaban N missing					
Antiplatelet	Valid N* No Yes N missing					
Type of antiplatelet	Valid N Aspirin Clopidogrel Prasugrel Ticlopidine Ticagrelor Cilostazol Triflusal Dipyridamole Others N missing					

*Number of events in each column.

One event could be associated with more than one treatment

Document: H:\HOR-Europe\2019\2512352 - Study on anticoagulation management - BI\Proyecto\Estadística\SAP\S
AP_REBELD_version1.0_08072020.docx

Author: [REDACTED] Version Number: Version 1.0
Version Date: [08072020]

Template No.: RWI_TP_BIOS0013 Revision 1

Reference: RWI_WI_BIOS0015

Effective Date: 15Jun2018

Table 47. Treatment received at the moment of thromboembolic events (2nd part)

		Pulmonary embolism	Stable angina	Unstable angina	Myocardial infarction with ST segment elevation	Myocardial infarction without ST segment elevation
Treatment (VKA/NOAC/antiplatelet)	Valid N* No Yes N missing					
VKA	Valid N* No Yes N missing					
Type of VKA	Valid N Acenocoumarol Warfarin N missing					
NOAC	Valid N* No Yes N missing					
Type of NOAC	Valid N Dabigatran Rivaroxaban Apixaban Edoxaban N missing					
Antiplatelet	Valid N* No Yes N missing					
Type of antiplatelet	Valid N Aspirin Clopidogrel Prasugrel Ticlopidine Ticagrelor Cilostazol					

Document: H:\HOR-Europe\2019\2512352 - Study on anticoagulation management - BI\Proyecto\Estadistica\SAP\S AP_REBELD_version1.0_08072020.docx

Author: [REDACTED] Version Number: Version 1.0
Version Date: [08072020]

Template No.: RWI_TP_BIOS0013 Revision 1

Reference: RWI_WI_BIOS0015

Effective Date: 15Jun2018

		Pulmonary embolism	Stable angina	Unstable angina	Myocardial infarction with ST segment elevation	Myocardial infarction without ST segment elevation
	Triflusal Dipyridamole Others N missing					

*Number of events in each column

One event could be associated with more than one treatment

Table 48. Treatment received at the moment of bleeding events (1st part)

		Intracranial	Digestive	Genitourinary	Gingival
Treatment (VKA/NOAC/antiplatelet)	Valid N* No Yes N missing				
VKA	Valid N* No Yes N missing				
Type of VKA	Valid N Acenocoumarol Warfarin N missing				
NOAC	Valid N* No Yes N missing				
Type of NOAC	Valid N Dabigatran Rivaroxaban Apixaban Edoxaban N missing				
Antiplatelet	Valid N*				

Document: H:\HOR-Europe\2019\2512352 - Study on anticoagulation management - BI\Proyecto\Estadística\SAP\SAP_REBELD_version1.0_08072020.docx

Author: [REDACTED]

Version Number:

Version 1.0

Version Date:

[08072020]

Template No.: RWI_TP_BIOS0013 Revision 1

Reference: RWI_WI_BIOS0015

Effective Date: 15Jun2018

		Intracranial	Digestive	Genitourinary	Gingival
	No Yes N missing				
Type of antiplatelet	Valid N Aspirin Clopidogrel Prasugrel Ticlopidine Ticagrelor Cilostazol Triflusal Dipyridamole Others N missing				

*Number of events in each column

One event could be associated with more than one treatment

Table 49. Treatment received at the moment of thromboembolic events (2nd part)

		Nasal	Pulmonary	Articular-muscular	Conjunctival
Treatment (VKA/NOAC/antiplatelet)	Valid N* No Yes N missing				
VKA	Valid N* No Yes N missing				
Type of VKA	Valid N Acenocoumarol Warfarin N missing				
NOAC	Valid N* No				

Document: H:\HOR-Europe\2019\2512352 - Study on anticoagulation management - BI\Proyecto\Estadística\SAP\SAP_REBELD_version1.0_08072020.docx

Author: [REDACTED] Version Number: Version 1.0
Version Date: [08072020]

Template No.: RWI_TP_BIOS0013 Revision 1

Reference: RWI_WI_BIOS0015

Effective Date: 15Jun2018

		Nasal	Pulmonary	Articular-muscular	Conjunctival
	Yes N missing				
Type of NOAC	Valid N Dabigatran Rivaroxaban Apixaban Edoxaban N missing				
Antiplatelet	Valid N* No Yes N missing				
Type of antiplatelet	Valid N Aspirin Clopidogrel Prasugrel Ticlopidine Ticagrelor Cilostazol Triflusal Dipyridamole Others N missing				

*Number of events in each column

One event could be associated with more than one treatment

Table 50. Current NOAC dose according to HAS-BLED

		HAS-BLED			
		Low risk	Intermediate risk	High risk	Total
Dabigatran dose	Valid N 110mg BID 150mg BID N missing				
Rivaroxaban dose	Valid N				

Document: H:\HOR-Europe\2019\2512352 - Study on anticoagulation management - BI\Proyecto\Estadística\SAP\SAP_REBELD_version1.0_08072020.docx

Author: [REDACTED] Version Number: Version 1.0
Version Date: [08072020]

Template No.: RWI_TP_BIOS0013 Revision 1

Reference: RWI_WI_BIOS0015

Effective Date: 15Jun2018

		HAS-BLED			
		Low risk	Intermediate risk	High risk	Total
	15mg QD 20mg QD N missing				
Apixaban dose	Valid N 2.5mg BID 5mg BID N missing				
Edoxaban dose	Valid N 30mg QD 60mg QD N missing				

Table 51. Overdosing and underdosing of current NOACs

		Appropriately dosed (n,%)	Underdosed (n,%)	Overdosed (n,%)
Dabigatran	Dabigatran (Age <80 years)			NA
	Dabigatran (Age ≥80 years)		NA	
	Dabigatran (75-79 years and HAS-BLED < 3)			NA
	Dabigatran (75-79 years and HAS-BLED ≥ 3)		NA	
	Dabigatran (creatinine clearance >50mL/min)			NA
	Dabigatran (creatinine clearance 30-50mL/min)			NA
Rivaroxaban	Rivaroxaban (creatinine clearance >50mL/min)			NA

Document: H:\HOR-Europe\2019\2512352 - Study on anticoagulation management - BI\Proyecto\Estadística\SAP\S AP_REBELD_version1.0_08072020.docx

Author: [REDACTED] Version Number: Version 1.0
Version Date: [08072020]

Template No.: RWI_TP_BIOS0013 Revision 1

Reference: RWI_WI_BIOS0015

Effective Date: 15Jun2018

		Appropriately dosed (n,%)	Underdosed (n,%)	Overdosed (n,%)
	Rivaroxaban (creatinine clearance ≤ 50 mL/min)		NA	
Apixaban	Apixaban (Age < 80 years)			NA
	Apixaban (Age ≥ 80 years)		NA	
	Apixaban (Body weight > 60 kg)			NA
	Apixaban (Body weight ≤ 60 kg)		NA	
	Apixaban (Serum creatinine $< 1,5$ mg/dl or creatinine clearance ≥ 30 mL/min)			NA
	Apixaban (Serum creatinine $\geq 1,5$ mg/dl or creatinine clearance < 30 mL/min)		NA	
Edoxaban	Edoxaban (Body weight > 60 kg)			NA
	Edoxaban (Body weight ≤ 60 kg)		NA	
	Edoxaban (creatinine clearance > 50 mL/min)			NA
	Edoxaban (creatinine clearance 15-50 mL/min)		NA	

Table 52. HAS-BLED score according NOAC+antiplatelet current treatment

		HAS-BLED score				
		Valid N	< 3	3-5	≥ 5	N missing
Current treatment	Dabigatran+aspirin					
	Dabigatran+clopidogrel					
	Dabigatran+peasugrel					
	...					
	... (for all combinations)					

Row percentage will be calculated

Document: H:\HOR-Europe\2019\2512352 - Study on anticoagulation management - BI\Proyecto\Estadistica\SAP\S AP_REBELD_version1.0_08072020.docx

Author: [REDACTED]

Version Number:

Version 1.0

Version Date:

[08072020]

Template No.: RWI_TP_BIOS0013 Revision 1

Reference: RWI_WI_BIOS0015

Effective Date: 15Jun2018

Table 53. Multivariate logistic model to evaluate the association between the Clinical Frailty Scale and the thromboembolic and the bleeding events

Variable	Estimate	Standard error	t-value	Pr> t	OR

*dependent variable: CFS in two categories: Frailty patients - CFS scoring >4 vs Non-frailty patients - CFS scoring ≤4)

*independent variables: thromboembolic and bleeding events. Other factors will be age, sex, BMI, smoking habit, alcohol consumption, time since NVAF diagnosis, NVAF type, modified EHRA scale, procedures and interventions, comorbidity Charlson index and clinical risk factors. Univariate analysis will be performed and all variables which have a P value of less than 0.1 will be included in the multivariate analysis.

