7.2.17 Underdosed or overdosed patient (current NOAC treatment)

The recommended dose of dabigatran is 150mg twice a day (BID). Patients who meet any of the following criteria should perform a dose adjustment to 110mg BID, so those who receive the recommended dose of 150mg BID will be classified as overdosed. Those who receive a 110mg BID dose and do not meet any of the following criteria will be classified as underdosed:

- Age ≥ 80 years
- Patients aged 75-79 years and HAS-BLED ≥ 3
- Moderate renal impairment (creatinine clearance 30-50mL/min)

The recommended dose of rivaroxaban is 20mg once a day (QD). Patients who meet the following criteria should perform a dose adjustment to 15mg QD, so those who receive the recommended dose of 20mg QD will be classified as overdosed. Those who receive a 15mg QD dose and do not meet following criteria will be classified as underdosed:

- Moderate renal impairment (creatinine clearance 30-50mL/min) or severe renal impairment (creatinine clearance 15-29mL/min)

The recommended dose of apixaban is 5mg BID. Patients who meet at least 2 of the following 3 criteria should perform a dose adjustment to 2.5mg BID, so those who receive the

Document:	H:\HOR-Europe\2019\2512352 - Study on anticoagulation management - BI\Proyecto\Estadistica\SAP\S		
	AP_REBELD_version1.0_08072020.docx		
Author:		Version Number:	Version 1.0
		Version Date:	[08072020]

Template No.: RWI_TP_BIOS0013 Revision 1

Reference: RWI_WI_BIOS0015

Effective Date: 15Jun2018

recommended dose of 5mg BID will be classified as overdosed. Those who receive a 2.5mg BID dose and do not meet at least 2 of the 3 following criteria will be classified as underdosed:

- Age \geq 80 years
- Body weight \leq 60 kg
- Serum creatinine \geq 1,5 mg/dl or severe renal impairment (creatinine clearance 15-29mL/min)

The recommended dose of edoxaban is 60mg OD. Patients who meet at least 1 of the following 2 criteria should perform a dose adjustment to 30mg OD, so those who receive the recommended dose of 60mg OD will be classified as overdosed. Those who receive a 30mg OD dose and do not meet at least 1 of the 2 following criteria will be classified as underdosed:

- Body weight \leq 60 kg
- Moderate or severe renal impairment (creatinine clearance 15-50mL/min)

A categorical variable for dose category with 3 levels will be described:

- 1) Appropriately dosed
- 2) Underdosed
- 3) Overdosed.

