14.6 Exploratory analysis

History and current antiplatelet treatment will be described by current NOAC type.

Treatment received at the time of thromboembolic and bleeding events will be described, including NOAC, VKA and antiplatelet treatments.

Doses of current NOAC treatment received by the patient will be described according to HAS-BLED score (as low, intermediate and high risk).

The percentage of underdosed and overdosed patients for current NOAC treatment will be described.

HAS-BLED total score (as <3 , $3-5$, ≥ 5) will be described according to NOAC and antiplatelet current treatment.

Multivariate logistic regression will be used to evaluate the association between the Clinical Frailty Scale (dependent variable: Frailty patients - CFS scoring >4 vs Non-frailty patients - CFS scoring ≤ 4) and the thromboembolic and the bleeding events (independent variables). To calculate this analysis, only events that have occurred subsequent to the start of anticoagulant therapy (not those prior to the start of VKA / NOACs) will be considered. Other factors will be age, sex, BMI, smoking habit, alcohol consumption, time since NVAf diagnosis, NVAf type, modified EHRA scale, procedures and interventions, comorbidity Charlson index and clinical risk factors. Univariate analysis will be performed. All variables which have a P value of less than 0.1 will be included in the multivariate analysis.

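### Exploratory Table 51 in the SAP conflicts with the joint dosing rule in 7.2.17: at least 11 of its 18 pre-filled NA cells can hold patients, and no row gives the under- and overdosed percentage

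*SAP*

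**What the plan says.** SAP 7.2.17 defines the dose classes for current NOAC treatment.

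- **Dabigatran:** patients meeting any one of three criteria (age 80 or over; age 75-79 with HAS-BLED 3 or more; creatinine clearance (CrCl) 30-50) "should perform a dose adjustment to 110mg BID, so those who receive the recommended dose of 150mg BID will be classified as overdosed".
- **Rivaroxaban:** the one criterion is CrCl 30-50 or 15-29. "Those who receive a 15mg QD dose and do not meet following criteria will be classified as underdosed".
- **Apixaban:** the criteria are age 80 or over; weight 60 kg or less; creatinine 1.5 or more, or CrCl 15-29. "Those who receive a 2.5mg BID dose and do not meet at least 2 of the 3 following criteria will be classified as underdosed".
- **Edoxaban:** one of two criteria is enough (weight 60 kg or less; CrCl 15-50).

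The section ends with a single derived variable: "A categorical variable for dose category with 3 levels will be described". SAP 14.6 commits to the result: "The percentage of underdosed and overdosed patients for current NOAC treatment will be described".

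The shell for this result is Table 51 in SAP 17.4. Its columns are appropriately dosed, underdosed and overdosed. Each row takes one criterion for one drug (one dabigatran pair combines age and HAS-BLED), and each row has one cell already marked NA. In the row "Dabigatran (creatinine clearance 30-50mL/min"), for example, the NA is printed under Overdosed. SAP section 9 says that the shells set the format and content of the output.

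**The concern.** An NA in a shell tells the programmer that nobody can fall in that cell. Here the NAs were placed as if the row's own criterion settled the correct dose. For three of the four drugs it does not, because 7.2.17 combines criteria. A programmer therefore has two instructions that disagree. If the shell is followed, a mis-dosed patient is either dropped from a row or counted there as appropriately dosed, while the same patient appears as mis-dosed in another row.

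The rows also cannot be added up to the promised percentage, since each patient enters several rows for the same drug. Table 51 is the only shell that reports under- and overdosing, and the protocol's rationale (section 7) names underdosing in this population as a reason for the study.

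**Working it through.** **Inputs.** The dose rules are from SAP 7.2.17, the rows and NA positions from Table 51, and the Cockcroft-Gault formula from SAP 7.2.4.2: CrCl = (140 - age) × weight × (0.85 if female) / (72 × creatinine).

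**Count of NA cells.** There is one per row: dabigatran 6 + rivaroxaban 2 + apixaban 6 + edoxaban 4 = 18.

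**Check.** For each row, look for a patient who belongs in it and whom 7.2.17 places in the NA column.

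| Row | NA under | Patient whom 7.2.17 puts there |
|---|---|---|
| Dabigatran, age <80 | Overdosed | 75 y, HAS-BLED 3, 150 mg |
| Dabigatran, age ≥80 | Underdosed | none |
| Dabigatran, 75-79, HAS-BLED <3 | Overdosed | CrCl 44, 150 mg |
| Dabigatran, 75-79, HAS-BLED ≥3 | Underdosed | none |
| Dabigatran, CrCl >50 | Overdosed | 75 y, HAS-BLED 3, CrCl 72, 150 mg |
| Dabigatran, CrCl 30-50 | Overdosed (as printed) | any patient on 150 mg |
| Rivaroxaban, CrCl >50 | Overdosed | none |
| Rivaroxaban, CrCl ≤50 | Underdosed | none if CrCl ≥15 |
| Apixaban, age <80 | Overdosed | 75 y, 50 kg, creatinine 1.5, 5 mg |
| Apixaban, age ≥80 | Underdosed | 80 y, 62 kg, creatinine 0.5, 2.5 mg |
| Apixaban, >60 kg | Overdosed | 80 y, creatinine 1.5, 5 mg |
| Apixaban, ≤60 kg | Underdosed | 75 y, creatinine 0.5, 2.5 mg |
| Apixaban, lower-creatinine row | Overdosed | 80 y, 40 kg, creatinine 0.5, 5 mg |
| Apixaban, higher-creatinine row | Underdosed | 75 y, 62 kg, creatinine 1.5, 2.5 mg |
| Edoxaban, >60 kg | Overdosed | CrCl 48, 60 mg |
| Edoxaban, ≤60 kg | Underdosed | none |
| Edoxaban, CrCl >50 | Overdosed | 40 kg, 60 mg |
| Edoxaban, CrCl 15-50 | Underdosed | none |

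**Sum.**
- As printed, with CrCl at least 15: 4 + 0 + 6 + 2 = 12.
- If the NA in the dabigatran CrCl 30-50 row belongs under Underdosed: 3 + 0 + 6 + 2 = 11.
- If patients on rivaroxaban with CrCl below 15 are in the analysis set and classified literally, one more cell is added: 13 as printed, or 12 with the dabigatran NA moved. Example: a woman of 85, 60 kg, creatinine 2.8 has CrCl (140 - 85) × 60 × 0.85 / (72 × 2.8) = 13.9. On 15 mg she meets no listed criterion, so she is underdosed, but that cell is NA in the only row she enters.

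The same 11 cells appear in all four cases.

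**Apixaban in detail.** In the row "Apixaban (Age ≥ 80 years"), Underdosed is NA. A patient in that row with no other criterion meets 1 of 3, so 2.5 mg is underdosing by 7.2.17. Three criteria and two doses give 8 mis-dosed combinations: 2.5 mg with none or exactly one criterion (1 + 3 = 4), and 5 mg with exactly two or all three (3 + 1 = 4).
- 2.5 mg with exactly one criterion: all 3 meet an NA, in the row of the criterion they have.
- 5 mg with exactly two criteria: all 3 meet an NA, in the row of the criterion they lack.
- 5 mg with all three criteria: can meet an NA, because the two renal rows overlap. The lower row is joined by "or creatinine clearance ≥ 30 mL/min", so a woman of 88, 50 kg, creatinine 1.2, with CrCl (140 - 88) × 50 × 0.85 / (72 × 1.2) = 25.6, enters both rows, and Overdosed is NA in the lower one.
- 2.5 mg with no criterion: meets none.

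That makes 3 + 3 + 1 = 7 of 8 as printed. With complementary renal rows it would be 6 of 8, and all 6 apixaban NA cells could still hold patients.

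**The promised percentage.** No row in Table 51 is a total for a drug or for all patients.

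**The case against.** The best defence is that each row judges the dose by its own criterion alone. That explains 17 of the 18 NAs; only the dabigatran CrCl 30-50 row departs from it. So 11 is the minimum only when patients are classified by 7.2.17. But 7.2.17 defines no criterion-by-criterion variable, and the reading contradicts its text, most plainly apixaban's two-of-three rule. An apixaban patient over 60 kg and aged 80 or more, with no renal criterion, on 2.5 mg would be appropriately dosed in the age row and underdosed in the weight row.

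A second defence is that the text is enough. SAP 7.2.17 is explicit, 14.6 commits to the percentage, and section 8 provides frequencies and percentages for categorical variables. This stands as a limit on the weight: a programmer has what is needed to derive the result, and only the shell lacks the row.

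Two stronger readings are tempting.

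- A reader might take 12 or 13 as the firm count. The twelfth cell rests on one NA that breaks the table's own pattern and may be a slip or a column shift from the PDF. The thirteenth needs rivaroxaban patients with CrCl below 15. Exclusion criterion 2 may remove them, but that depends on the SmPCs, which are not in the documents. The category below 15 in 7.2.4.2 belongs to a general staging list and does not show that such patients are expected.
- A reader might infer that mis-dosed patients disappear from the table. Affected apixaban and edoxaban patients still have an open cell in another row. Only one dabigatran group (150 mg, age 75-79, HAS-BLED below 3, CrCl 30-50) would have none, and only if the doubtful NA stands as printed. The one other such group is the conditional rivaroxaban group above.

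**Conclusion.** Table 51 does not fit the rule it is meant to report. With patients classified by 7.2.17, at least 11 of the 18 NA cells can hold patients: all 6 for apixaban, 3 for dabigatran (age below 80; 75-79 with HAS-BLED below 3; CrCl above 50) and 2 for edoxaban (above 60 kg; CrCl above 50). The dabigatran CrCl 30-50 cell is a possible addition, and the rivaroxaban cell a conditional one. The overlapping apixaban renal rows and the missing total rows are separate faults in the same shell.

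The size is minor. The analysis is exploratory and was added after the protocol (SAP 4.6), the derivation itself is clear, and primary and secondary outcomes do not depend on it. The counts are of cells and combinations, not patients; how many patients would be affected cannot be derived from the documents.

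**What to change.** 1. Derive the 7.2.17 variable once per patient.
2. Add to Table 51 one row per NOAC and a total row, with n (%) appropriately dosed, underdosed, overdosed and missing.
3. Keep the criterion rows only as a breakdown, with NA only where 7.2.17 makes the cell impossible:
   - Underdosed: dabigatran age ≥80, dabigatran 75-79 with HAS-BLED ≥3, dabigatran CrCl 30-50 (not Overdosed), edoxaban ≤60 kg, edoxaban CrCl 15-50.
   - Overdosed: rivaroxaban CrCl >50.
   - Underdosed for rivaroxaban CrCl ≤50 only if patients with CrCl below 15 cannot be in the analysis set. State in 7.2.17 how CrCl below the listed ranges is classified.
4. Make the apixaban renal rows complementary: creatinine <1.5 and CrCl ≥30, against creatinine ≥1.5 or CrCl <30.

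The cost is a revised shell and its programming. The variable and its inputs are already planned, and no new data are needed.

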7.2.4.2 Creatinine clearance

Creatinine clearance will be estimated using Cockcroft-Gault formula (7):

$$CCr = (140 - \text{Age}(\text{years})) \times \text{Weight} (\text{kg}) \times [0.85 \text{ if female}] / 72 \times [\text{Serum Creatinine} (\text{mg/dL})]$$

Chronic Kidney Disease will be categorized according to these values, included in Clinical Practice Guidelines for Chronic Kidney Disease: Evaluation, Classification, and Stratification:

- ≥ 90 : Kidney damage with normal or increased glomerular filtration rate (GFR)
- 60-89: Kidney damage with mild decreased GFR
- 30-59: Moderate decrease in GFR
- 15-29: Severe decrease in GFR
- < 15 : Kidney failure

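### SAP Table 51: both apixaban renal rows are joined with 'or', so a patient meeting exactly one renal condition is counted both with and without the renal criterion

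*SAP*

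**What the plan says.** SAP 7.2.17 sets three apixaban criteria (age, weight, renal) and classifies dose by how many are met: "The recommended dose of apixaban is 5mg BID. Patients who meet at least 2 of the following 3 criteria" call for the adjusted dose. The renal criterion is serum creatinine at or above "1,5 mg/dl or severe renal impairment (creatinine clearance 15-29mL/min"). Either limb is enough, and together they count as one criterion of the three. Every patient then receives a single classification: "A categorical variable for dose category with 3 levels will be described", namely appropriately dosed, underdosed or overdosed. Clearance comes from SAP 7.2.4.2: "Creatinine clearance will be estimated using Cockcroft-Gault formula (7").

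Table 51 (SAP 17.4) breaks the apixaban result down in pairs of rows. Both rows of the renal pair contain the words "mg/dl or creatinine clearance". The pair reads:

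- first row, criterion not met: "Apixaban (Serum creatinine $< 1,5$ mg/dl or creatinine clearance ≥ 30 mL/min"), with the Overdosed cell pre-filled NA;
- second row, criterion met: "Apixaban (Serum creatinine $\geq 1,5$ mg/dl or creatinine clearance < 30 mL/min"), with the Underdosed cell pre-filled NA.

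**The concern.** The second row follows 7.2.17 in using 'or'. The first row is its counterpart, but it reverses the two inequalities and keeps 'or', so it means 'not both conditions' where it should mean 'neither condition'.

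The pair is evidently meant as a split. The other two apixaban pairs (age below 80 against 80 and over; weight above 60 kg against 60 kg or less) are exact complements. Every other pair in Table 51 is at least mutually exclusive. Where the SAP intends multiple counting it says so: Tables 46-49 note that one event may be linked to several treatments, and the safety tables label items as multi-response. Table 51 carries no such note, and no tie rule appears elsewhere.

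The renal breakdown of apixaban dosing is at stake. Coded as written, the 'not met' row contains patients who have the criterion. A programmer who notices the overlap has to invent an undocumented rule.

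**Working it through.** There is no plan figure to reproduce. The check is one of logic, followed by the SAP's own clearance formula and an illustration of size.

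**1. Logic.** Let A = creatinine ≥1.5 mg/dl and B = clearance <30 mL/min (Table 51 cut-offs).

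- Second row: A or B.
- First row as printed: (not A) or (not B), which equals not (A and B).
- Complement of the second row: (not A) and (not B).
- Overlap of the printed rows: exactly one of A and B is true.
- Every patient falls in at least one row, so first-row count + second-row count = number of patients + overlap.

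| Case (creatinine, clearance) | First row, printed | Second row | First row with 'and' |
|---|---|---|---|
| Neither (1.0, 50) | yes | no | yes |
| Creatinine only (1.6, 40) | yes | yes | no |
| Clearance only (1.2, 25) | yes | yes | no |
| Both (1.8, 20) | no | yes | no |

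With 'and', the two rows are exclusive and exhaustive.

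**2. Whether such patients occur.** Cockcroft-Gault (SAP 7.2.4.2) is (140 − age) × weight × [0.85 if female] / (72 × creatinine). Age, weight and sex enter, so creatinine and clearance can fall on opposite sides of their cut-offs.

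- Man, 78 years, 80 kg, creatinine 1.6: 62 × 80 / (72 × 1.6) = 4960 / 115.2 = 43.1. A holds, B does not: both rows.
- Woman, 88 years, 50 kg, creatinine 1.2: 52 × 50 × 0.85 / (72 × 1.2) = 2210 / 86.4 = 25.6. B holds, A does not: both rows.

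Both meet the 7.2.17 renal criterion and belong only in the second row.

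**3. Size, under assumed distributions.** None of these inputs is in the documents: age uniform 75-92, half women, mean weight 67 kg (women) and 77 kg (men) with SD 12 kg, log-normal creatinine with median 0.9-1.4 mg/dl and log-SD 0.25-0.45, 400,000 draws per scenario. The extremes are:

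| Median, log-SD | In both rows | Share of second row also in first |
|---|---|---|
| 0.9, 0.25 | 4% | 82% |
| 1.4, 0.25 | 25% | 54% |
| 1.4, 0.45 | 17% | 36% |

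Across the grid, 4-25% of apixaban patients fall in both rows, or 36-82% of the 'met' row.

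**4. Interaction with the NA cells.** Dose category depends on at least two of three criteria, so neither NA is safe.

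- The man above meets only the renal criterion. On 2.5 mg BID, 7.2.17 classes him as underdosed. Once the connector is corrected he sits only in the second row, where Underdosed is NA.
- The woman meets all three criteria. On 5 mg BID, 7.2.17 classes her as overdosed. As printed she is also in the first row, where Overdosed is NA.
- A patient aged 80 or over, weighing 60 kg or less and without the renal criterion, is overdosed on 5 mg BID under 7.2.17. That patient stays in the first row after the correction and has no cell there.

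**The case against.** The best case for leaving this as an editorial matter is its narrow reach. Table 51 is a mock table for an exploratory description that SAP 4.6 lists as added after the protocol. The dose category is defined in 7.2.17 from the criterion itself. A programmer who derives a renal flag from that section and tabulates yes against no never meets the overlap. That stands, and it limits the seriousness. It does not make the shell right, since the shell is what SAP section 9 says fixes the format and content of the output.

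A second objection is that changing one word is not a complete repair: the corrected row can leave a patient with no usable cell (step 4 of the working). That also stands, and the NA cells have to be handled in the same edit.

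Four stronger readings are tempting, and the documents do not support them.

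- A reader might infer that the overdosed percentage of the 'not met' row is diluted. That cell is NA, so no such percentage is reported. Only the appropriately dosed and underdosed cells are affected.
- A reader might infer that 'and' makes the first row the exact complement of the 7.2.17 criterion. It complements Table 51's second row, which uses clearance below 30. Section 7.2.17 bounds that limb at 15-29, so a patient with creatinine below 1.5 and clearance below 15 is treated differently in the two places.
- A reader might infer that most patients with the criterion are double-counted. The share runs from 36% to 82% over the assumed range, so 'most' holds only for some inputs.
- A reader might infer that patients are misclassified or that a main result moves. No patient's 7.2.17 category changes.

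**Conclusion.** The two apixaban renal rows of Table 51 are not mutually exclusive, and the first is the faulty one, because 7.2.17 places a patient with exactly one limb on the 'met' side. This needs no assumption. Following the shell gives row denominators that exceed the apixaban total by the size of the overlap, and a 'not met' row that includes patients who have the criterion.

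The extent, about 4-25% of apixaban patients, is conditional on the assumed age, weight and creatinine distributions and is an illustration, not a forecast. The shift in any reported dosing percentage cannot be derived, since the documents give no dose mix by renal status. The damage is confined to one breakdown in one exploratory table; the overall dose category and the primary and secondary outcomes are untouched. It should be corrected before the table is programmed, as a point of modest weight.

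**What to change.** In Table 51, change 'or' to 'and' in the first apixaban renal row, so that it becomes the complement of the second row. Add a programmed check that the two rows sum to the number of apixaban patients whose renal criterion can be classified.

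In the same edit:

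- reconcile the clearance wording, which is below 30 in Table 51 and 15-29 in 7.2.17, so that row and criterion describe the same patients;
- replace the pre-filled NA cells in these two rows with counts from the 7.2.17 at-least-two-of-three classification, so that every patient has a cell.

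No clinical threshold is proposed here; the two sections have to be made to agree. The cost is one connector, one aligned phrase, two NA cells and one programming check, with no new data and no change to any other analysis.
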